13.2 MEASUREMENT OF RESPONSE

Assessment of clinical response will be made according to the guidelines as outlined above. The objective measures of response, such as bone marrow slides and CT scans, will be saved so that responses may be audited. Staging will include a CBC/differential, an interim history and physical examination with documentation of measurable disease, and performance status. Physical examination should record the diameter, in two planes, of the largest palpable nodes in each of the following sites: cervical, axillary, supraclavicular, inguinal, and femoral. Physical examination if relevant can record liver and spleen size as determined by measurement below the respective costal margin. A CT/MRI or U/S (in patients with an abnormal initial scan) will be done routinely after even cycle numbers (2, 4, 6, 8, 10) and will be done at other times if there is clinical evidence that the patient has had a PR, CR, or progressive disease.

13.3 CONFIRMATION OF RESPONSE & DURATION OF RESPONSE

13.3.1 Confirmation

The beginning of PR or CR will be considered the earliest time point where all relevant tests are consistent with CR or PR, respectively. CR or PR must be confirmed for at least 4 weeks according to the criteria above. For consideration of CR or PR duration based on the CBC, single unacceptable values preceded and followed by acceptable values, or values up to day 12 of each cycle may be ignored.

13.3.2 Duration of Response

In patients in CR, the bone marrow biopsy and CT scan should be done at least 4 weeks after the last dose of the last cycle, at 6 month intervals for 2 years after CR, and then at 1 year intervals, and if positive would indicate relapse rather than invalidation of the CR. The duration of PR or CR is measured from the date a confirmed CR or PR begins, until the date that staging studies are no longer consistent with CR or PR. The duration of overall response will be measured from the date that a confirmed response begins, until the date that recurrent or progressive disease is objectively documented.

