1.2 SECONDARY

- To describe the response duration.
- To describe how blood levels of LMB-2 (AUC, Cmax) are related to toxicity.
- To describe how the development of neutralizing antibodies affects blood levels of LMB-2 and toxicity.
- To describe how soluble Tac-peptide (sIL2Ra) levels correlate with response to treatment with LMB-2.

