Prognosis with standard therapy in HCL. Neither of the above-mentioned long term follow-up studies of CdA show a plateau in the disease-free survival curve [15, 16]. Moreover, patients who are in CR after purine analog therapy were found to have PCR-detectable HCL [22, 23]. Although purine analogs are highly effective even in relapsed patients with HCL, several large studies indicate declining CR rates and/or durations with each repeated course [15, 16, 24]. Lack of curability combined with declining efficacy with each retreatment points to eventual loss of ability to effectively treat the disease. Clearly many patients may die of other causes, but those who live long enough may be predicted to progress and eventually die of HCL-related pancytopenia. With over 15 years passing since the introduction of cladribine in the effective treatment of HCL, a significant number of patients with cladribine-resistant disease have accumulated over time, emphasizing the need for development of new approaches.

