2.4 RATIONALE OF STUDY DESIGN

- 2.4.1 CD25 expression in HCL. CD25 is expressed on about 75-80% of HCL samples [6]. LMB2 is a recombinant immunotoxin that targets CD25.
- 2.4.2 Response of HCL to LMB-2. In the phase I dose-escalation trial of LMB2, there were 1 CR and 3 PRs out of 4 HCL patients [70, 71]. Several of these responders could not be effectively retreated either because of neutralizing antibodies or disease-related infections.
- 2.4.3 Need for LMB-2 in HCL. BL22 is clearly the preferred agent for HCL due to 20-25% of patients who have CD25 negative HCL cells. Thus HCL patients eligible for LMB-2 would have already received BL22 and not be eligible or appropriate for further BL22. Such patients include 2 groups:
 - 2.4.3.1 Patients who had HUS from BL22. Currently 8 CD25+ HCL patients have had HUS from BL22. Several of these might be appropriate for further BL22 at a lower dose level, but since LMB-2 has never caused HUS, the dose they could receive of LMB-2 would be significantly higher and hence their chance of response much better.

2.4.3.2 Patients who did not completely respond to BL22 despite multiple cycles. A possible reason for lack of CR could be that since CD22 is expressed at such high levels in HCL (up to 100,000 sites/cell), patients with significant tumor burden could have very limited distribution of BL22 to all sites of tumor. HCL, while being very sensitive to LMB-2 [74], express only about 1300-17,000 sites/cell and the half-life is slightly longer than BL22. A total of 6 out of 31 patients on phase I and 5 out of 18 on phase II might have benefited from LMB-2 due to improved distribution. Several of these patients are still alive without neutralizing antibodies and might benefit by LMB-2.

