4.10 POST TREATMENT EVALUATION (OFF TREATMENT BUT ON STUDY)

Patients will be taken off treatment when they meet off treatment criteria. Patients who are off treatment due to toxicity will be followed until resolution of their side effects. On- or off-treatment patients who have not had progressive disease will be followed every 3-12 months until they have progressive disease (see Section 12, Study Calendar). Patients who have progressive disease may also need follow-up for other endpoints, including neutralizing antibodies (see Section 12, Study Calendar). Follow-up assessments will be conducted per PI discretion and may be obtained from clinic visits either at NIH or elsewhere.

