15.2 SAMPLE SIZE/ACCRUAL RATE

The primary objective of this trial will be to determine if LMB-2 can produce responses in a reasonable proportion of patients at the current dose and schedule and thus warrant further testing. Considering that patients have not been able to respond well to either cladribine or BL22, an overall response rate of 50% would be reasonable, and < 20% would be considered too low. The trial will be conducted using a Simon two-stage optimal design [\[75\]](#). With alpha=0.10 (the probability of incorrectly accepting a poor agent), and beta=0.10 (the probability of incorrectly rejecting a good agent), we will try to rule out an undesirably low response probability of 20% ($p_0=0.20$) in favor of a level indicative of acceptable activity, 50% ($p_1=0.50$).

Ten evaluable patients will initially be enrolled. If 0-2/10 demonstrate a CR/PR, then accrual will stop and the agent will be considered inactive. If 3+/10 patients have a CR/PR, accrual will continue until a total of 17 patients have been enrolled. If 3-5 of 17 have a CR/PR, this will be considered insufficient activity, and the agent will not be considered worthy of further development. If 6+/17 have a CR/PR, then the agent will be considered active (and at least potentially able to produce a CR/PR level consistent with 50%). In addition, if there are 6+/17 responding patients, up to 8 additional patients overall (maximum 25 evaluable patients overall) will be allowed to be entered into this trial to be enrolled to provide additional data for secondary endpoints. Confidence intervals will be constructed about the observed response proportions based on a two-stage approach [\[76\]](#). Under the null hypothesis ($p_0=0.20$), the probability of early termination of this trial is 0.68.

Duration of response is also important to evaluate in this population. A statistical summary of the duration of response will be reported, along with the fraction of responding patients who achieve a six month response duration, and the corresponding 95% confidence interval. In addition, a Kaplan-Meier curve of response duration will be created to illustrate the pattern associated with this outcome.

Abbreviated Title: LMB-2 for HCL

Version date: 02/07/2023

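### The response-duration rules in 13.3.2 have no death event, so applied as written they would ordinarily censor deaths in remission and the Kaplan-Meier curve in 15.2 would overstate durability

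*Combined protocol and SAP*

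**What the plan says.** Section 1.2 lists response duration first among the secondary objectives, in descriptive terms: "To describe the response duration".

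Section 13.3.2 gives two rules for when a response ends. The duration of a CR or PR runs "until the date that staging studies are no longer consistent with CR or PR". The duration of overall response runs "until the date that recurrent or progressive disease is objectively documented". Both name disease findings only.

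Section 15.2 plans a statistical summary of duration, "the fraction of responding patients who achieve a six month response duration" with a 95% confidence interval, and states that "a Kaplan-Meier curve of response duration will be created to illustrate the pattern associated with this outcome". It lists no events and no censoring rules.

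No other section fills the gap. Under 4.10, patients without progression "will be followed every 3-12 months until they have progressive disease". Death is not among the off-study criteria in 4.11, and 4.12 covers loss to follow-up only. Death is otherwise dealt with in safety reporting (7.3.2 and 8.3) and in the background.

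**The concern.** A Kaplan-Meier analysis has to code each responder as having an event or as censored. Someone who dies in remission meets neither end-of-response rule, so an analyst who follows 13.3.2 literally has no event to record and would normally censor at death. Censoring assumes that the patient could still have relapsed later at the same rate as those who remain at risk. After death that is impossible. The curve then describes durability as if responders did not die, and it looks best when early deaths are most frequent, including deaths to which treatment contributed.

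The protocol itself foresees such deaths over the long term. On prognosis, section 2.1 says "Clearly many patients may die of other causes". Response duration is the only planned time-to-event result, and 15.2 describes it as important in this population. If the coding is left open, it could be chosen after outcomes are known in a single-arm trial. The curve and the six-month fraction could also disagree at the same time point.

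**Working it through.** **The plan's own figures.** The documents state no number for response duration, so there is none to reproduce on this point. The nearest design figure is the probability of early termination under a 20% response rate: P(0 to 2 of 10) = 0.107 + 0.268 + 0.302 = 0.678, which agrees with the 0.68 in 15.2. Duration does not enter this calculation or the decision rule.

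**Inputs.** Section 15.2 gives 17 patients at the decision point, at most 25 evaluable, and a target response rate of 50%. That implies about 9 responders (0.5 × 17 = 8.5) or 13 (0.5 × 25 = 12.5). The numbers and times of deaths and relapses are assumptions: relapses at months 2 and 4, one death in remission at month 3, all others still in response at six months.

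**Formula.** The Kaplan-Meier estimate is the product over event times of (1 − 1/number at risk). A censored death leaves the risk set without adding a factor. A death counted as an event adds one.

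- 9 responders, death censored: 8/9 × 6/7 = 48/63 = 76%.
- 9 responders, death as event: 8/9 × 7/8 × 6/7 = 6/9 = 67%. Difference 9.5 points. The standard error of 6/9 is √(0.667 × 0.333/9) = 15.7 points, so the shift is 0.6 SE.
- 13 responders, death censored: 12/13 × 10/11 = 120/143 = 84%.
- 13 responders, death as event: 12/13 × 11/12 × 10/11 = 10/13 = 77%. Difference 7.0 points, SE 11.7, again 0.6 SE.

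**Other assumed counts.** One death at month 2, then one relapse at month 3:

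- 6 responders: 4/5 = 0.800 censored, 4/6 = 0.667 as event.
- 10 responders: 8/9 = 0.889 censored, 8/10 = 0.800 as event.
- 20 responders: 18/19 = 0.947 censored, 18/20 = 0.900 as event.

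A single early death is therefore worth about 5 to 13 points. With no deaths in remission the two codings give the same curve.

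**Average effect.** If death and relapse are independent, the expected gap at six months is the relapse-free probability times the six-month death risk. For assumed median times to relapse of 12 and 24 months (exponential), the relapse-free probability is 0.5^(6/12) = 0.71 and 0.5^(6/24) = 0.84. Death risks of 5%, 10% and 15% then give about 4, 7 to 8, and 11 to 13 points.

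**The six-month fraction.** Taken over all responders, it is 6/9 and 10/13 in the main examples, and 4/6, 8/10 and 18/20 in the others. Each equals the death-as-event value. It reaches a higher figure only if the dead patient is dropped (for example 8/9 instead of 8/10) or if it is read off the death-censored curve.

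**The case against.** The strongest reply is that the plan is silent and does not prescribe censoring. That is right: a reader might infer that the protocol instructs the analyst to censor deaths, but no sentence says so. Censoring is the ordinary consequence of an event definition that names disease findings only.

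A reader might also infer that the six-month fraction is biased upward. The documents do not support this. Section 15.2 describes a proportion of responding patients, and someone who dies in remission at month 3 has not reached six months. The percentages above apply to the Kaplan-Meier curve, which 15.2 offers as an illustration.

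The evidence for frequent early deaths in remission is thin, and this stands too. Section 2.4.2 says of the phase I patients: "Several of these responders could not be effectively retreated either because of neutralizing antibodies or disease-related infections". It reports no deaths and does not place the infections in remission. The cytopenias in 3.1.1.2 are an entry condition, whereas a response under 13.1 requires recovered or improved counts. The remark in 2.1 concerns long-term prognosis.

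Finally, the target could be relapse alone. The death-censored curve does not serve that aim either. With 9 responders its complement is 1 − 0.762 = 23.8%, against an actual relapse proportion of 2/9 = 22.2%.

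**Conclusion.** The point holds in a limited form. Neither 13.3.2 nor 15.2 lets death end a response, and applying those rules as written would ordinarily put the duration curve above the proportion of responders alive and in response. In the 9- and 13-responder examples the six-month estimate rises by 7 to 9.5 points, about 0.6 of a standard error. Across 6 to 20 responders the range is roughly 5 to 13 points for one early death. All of this is conditional on assumed deaths and relapses, because the documents give no rates.

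The six-month fraction is not shown to be inflated, but its handling of death should be written down. The consequence is confined to a descriptive secondary endpoint. It is still worth correcting: following the stated event definition gives a worse estimate than a standard rule that costs little.

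**What to change.** In 13.3.2, end response duration (CR, PR and overall) at the earliest of relapse, progression or death from any cause. In 15.2, use that event rule for the Kaplan-Meier curve, say when patients without an event are censored, and state that the six-month fraction has all responders in the denominator, with a death before six months counted as not achieving a six-month response. If a relapse-only estimate is also wanted, cumulative incidence of relapse with death in remission as a competing event would provide it; this is optional.

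The cost is a few sentences. The duration figure may be slightly less favourable. Dates of deaths in remission will also have to be recorded beyond the 30-day window used for reporting in 7.3.2 and 8.3, so the follow-up in 4.10 should collect them.

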14 DATA REPORTING / REGULATORY CONSIDERATIONS

Adverse event lists, guidelines, and instructions for AE reporting can be found in Section [7](#) (Adverse Events: List and Reporting Requirements).

14.1 PROCEDURES

This study will be monitored by Clinical Data Update System (CDUS) version 1.X. Cumulative CDUS data will submitted quarterly to CTEP by electronic means. Reports are due January 31, April 30, July 31, and October 31.

For data safety and monitoring, all adverse events will be reviewed by the Principal Investigator and the research team. The data manager and research nurses will be responsible for data entry and reporting. Unexpected adverse events and/or serious adverse events will be reported to the NCI IRB and the study sponsor as described in section [7](#). If trends are noted and/or risks warrant it, accrual will be interrupted and/or the protocol and/or consent document will be amended accordingly.

14.2 STUDY SPONSOR: CTEP

15 STATISTICAL CONSIDERATIONS

15.1 STUDY DESIGN/ENDPOINTS

This is a nonrandomized phase II study. The primary objective is to 1) determine the response rate of LMB-2 in patients with CD25-positive Hairy Cell Leukemia (HCL).

15.2 SAMPLE SIZE/ACCRUAL RATE

The primary objective of this trial will be to determine if LMB-2 can produce responses in a reasonable proportion of patients at the current dose and schedule and thus warrant further testing. Considering that patients have not been able to respond well to either cladribine or BL22, an overall response rate of 50% would be reasonable, and < 20% would be considered too low. The trial will be conducted using a Simon two-stage optimal design [\[75\]](#). With alpha=0.10 (the probability of incorrectly accepting a poor agent), and beta=0.10 (the probability of incorrectly rejecting a good agent), we will try to rule out an undesirably low response probability of 20% ($p_0=0.20$) in favor of a level indicative of acceptable activity, 50% ($p_1=0.50$).

Ten evaluable patients will initially be enrolled. If 0-2/10 demonstrate a CR/PR, then accrual will stop and the agent will be considered inactive. If 3+/10 patients have a CR/PR, accrual will continue until a total of 17 patients have been enrolled. If 3-5 of 17 have a CR/PR, this will be considered insufficient activity, and the agent will not be considered worthy of further development. If 6+/17 have a CR/PR, then the agent will be considered active (and at least potentially able to produce a CR/PR level consistent with 50%). In addition, if there are 6+/17 responding patients, up to 8 additional patients overall (maximum 25 evaluable patients overall) will be allowed to be entered into this trial to be enrolled to provide additional data for secondary endpoints. Confidence intervals will be constructed about the observed response proportions based on a two-stage approach [\[76\]](#). Under the null hypothesis ($p_0=0.20$), the probability of early termination of this trial is 0.68.

Duration of response is also important to evaluate in this population. A statistical summary of the duration of response will be reported, along with the fraction of responding patients who achieve a six month response duration, and the corresponding 95% confidence interval. In addition, a Kaplan-Meier curve of response duration will be created to illustrate the pattern associated with this outcome.

Abbreviated Title: LMB-2 for HCL

Version date: 02/07/2023

It is expected that 5-10 patients per year can be recruited for enrollment onto this trial. With a goal of 25 evaluable patients, it is expected that 4 years is a reasonable time frame in which to accrue all needed subjects. The accrual ceiling will be 55 to account for inevaluable participants and screen failures..

Due to LMB-2 supply, no more than a total of 13 patients may be accrued to the protocol until a new clinical lot is ready for use in patients.

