4.11 OFF-STUDY CRITERIA

- Screen failure
- Patient begins another LMB trial which allows data collection
- Unwillingness to continue follow-up or provide follow-up data.

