4.12 LOST TO FOLLOW-UP

A participant will be considered lost to follow-up if he or she fails to return for 3 consecutive scheduled visits and is unable to be contacted by the study site staff.

The following actions must be taken if a participant fails to return to the clinic for a required study visit:

- The site will attempt to contact the participant and reschedule the missed visit within 2 weeks and counsel the participant on the importance of maintaining the assigned visit schedule and ascertain if the participant wishes to and/or should continue in the study.
- Before a participant is deemed lost to follow-up, the investigator or designee will make every effort to regain contact with the participant (where possible, 3 telephone calls and, if necessary, a certified letter to the participant's last known mailing address or local equivalent methods). These contact attempts should be documented in the participant's medical record or study file.
- Should the participant continue to be unreachable, he or she will be considered to have withdrawn from the study with a primary reason of lost to follow-up.

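### Section 15.2 gives no rule for responders whose follow-up ends in remission before month 6, so the six-month fraction is undefined for them and, read literally, would be biased downward

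*Combined protocol and SAP*

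**What the plan says.** Response duration is the first secondary objective in section 1.2: "To describe the response duration". Section 13.3.2 measures overall response from the start of a confirmed response "until the date that recurrent or progressive disease is objectively documented" and gives no censoring rule.

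Section 15.2 plans three things for this endpoint: a statistical summary; a six-month result, "along with the fraction of responding patients who achieve a six month response duration, and the corresponding 95% confidence interval"; and, in addition, "a Kaplan-Meier curve of response duration will be created to illustrate the pattern associated with this outcome". The six-month fraction is the only duration result for which an interval is specified. No interval method is named, and no Kaplan-Meier value at six months is requested.

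On follow-up, section 4.10 says: "On- or off-treatment patients who have not had progressive disease will be followed every 3-12 months until they have progressive disease". Observation can end without relapse. Section 4.11 takes patients off study for "Unwillingness to continue follow-up or provide follow-up data", and under section 4.12 a patient who cannot be reached ends as follows: "he or she will be considered to have withdrawn from the study with a primary reason of lost to follow-up". Section 4.11 also lists "Patient begins another LMB trial which allows data collection".

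**The concern.** A responder last assessed in remission at month 3 and then lost has no documented six-month duration, but has not relapsed either. The plan does not say whether this patient counts as a failure, is left out, or is censored.

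The most literal reading is a simple proportion: responders form the denominator, and only those shown to reach six months form the numerator. Under that reading an incomplete remission counts the same as a relapse. The Kaplan-Meier method, which treats the two differently, is planned only as an illustration.

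The number of responders will be small, so one patient matters. Leaving the rule open also means it could be chosen after the data are seen.

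**Working it through.** **The plan's own figure.** Section 15.2 states no figure for the six-month result. Its one calculated figure, the probability of early termination under p0 = 0.20, reproduces: P(X ≤ 2 | n = 10, p = 0.20) = 0.678, stated as 0.68. The point below does not touch that design.

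**Inputs.** From section 15.2: at least 6 responders of 17 for the agent to be called active, and at most 25 evaluable patients, so about 12 responders at the 50% target rate (0.50 × 25 = 12.5). Assumed, because the documents do not give them: a true six-month rate S(6) of 75% or 80%, and a proportion c leaving follow-up by month 6 of 5, 10 or 20%, independent of relapse, with exponential times.

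**Weight of one patient.** 1/6 = 16.7 points with 6 responders; 1/12 = 8.3 points with 12.

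**Reading A: counted as not achieving six months.** A responder counts only if neither relapse nor departure occurs by month 6.

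- Expected fraction = S(6) × (1 − c)
- Bias = −S(6) × c
- At S(6) = 0.75: −3.75, −7.5 and −15 points for c = 5, 10 and 20%

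**Reading B: excluded.** Let λ = −ln S(6)/6, μ = −ln(1 − c)/6, and let Pe = λ/(λ + μ) × [1 − S(6)(1 − c)] be the probability that relapse is seen before departure and by month 6.

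- Expected fraction ≈ S(6)(1 − c) / [S(6)(1 − c) + Pe]
- Example, S(6) = 0.80 and c = 10%: Pe = 0.2231/(0.2231 + 0.1054) × 0.28 = 0.190, giving 0.72/0.910 = 0.791

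Both readings at S(6) = 0.80:

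| c | A: counted as failure | B: excluded | Kaplan-Meier target |
|---|---|---|---|
| 0% | 0.800 | 0.800 | 0.800 |
| 5% | 0.760 | 0.796 | 0.800 |
| 10% | 0.720 | 0.791 | 0.800 |
| 20% | 0.640 | 0.780 | 0.800 |

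Exclusion also falls below the truth, because observed early relapses stay in while early incomplete remissions are dropped. The shortfall is only about 0.4 to 2 points.

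**Worked record (hypothetical).** Twelve responders: relapses at months 3 and 5, two leaving in remission at months 2 and 4, eight followed beyond month 6.

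- Reading A: 8/12 = 67%, exact 95% CI 35 to 90%
- Reading B: 8/10 = 80%
- Kaplan-Meier: 11 at risk at month 3 and 9 at month 5, so (1 − 1/11) × (1 − 1/9) = 10/11 × 8/9 = 0.808
- Greenwood sum for Kaplan-Meier: 1/(11 × 10) + 1/(9 × 8) = 0.0230; log-log 95% CI about 42 to 95%

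The same data give 67%, 80% or 81% according to a rule the plan does not state.

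**The case against.** A reader might infer that the plan scores early leavers as failures and that its six-month result is therefore biased downward. The documents do not support that. No section states such a rule. Section 15.2 names neither an estimator nor a denominator rule, and exclusion fits its wording too. Reading the fraction off the Kaplan-Meier curve is also possible, though strained, since the curve is listed separately.

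The case against goes further, and much of it stands.

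- **Early loss may be rare.** Cycles run every 28 days for up to six, with staging before each (sections 4.1 and 4.4.1). Follow-up data may come from outside NIH (section 4.10). Repeated contact attempts precede a declaration of loss (section 4.12). Patients in CR have marrow and CT at six-month intervals for two years (section 13.3.2).
- **Entry to another LMB trial is a weak example.** The criterion is limited to trials that permit data collection, so outcome information may continue. The point rests on withdrawal and loss to follow-up.
- **The intervals in the worked record overlap almost entirely.** The record also loses 2 of 12 (17%), near the top of the assumed range.
- **The net direction is not certain.** Visits 3 to 12 months apart can detect relapse late and push the result upward. This affects the Kaplan-Meier estimate and the crude fraction alike, so it is no reason to leave the censoring rule open. If departures are related to relapse, Kaplan-Meier can overstate duration, and counting leavers as failures is then a conservative bound.
- **A censoring-aware display is already planned.** The curve will sit beside the fraction. What is missing is a six-month value from it with an interval.

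**Conclusion.** The point holds as a gap in specification with a conditional bias. Section 15.2 reports a six-month fraction with a 95% CI, and no section says how a responder with incomplete follow-up before month 6 enters it. Under the literal reading the downward bias is S(6) × c: about 4, 8 or 15 points for losses of 5, 10 or 20% at a true rate of 75%. Under exclusion it is about 0.4 to 2 points at a true rate of 80%. With no early loss it is zero.

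These sizes rest on assumed rates and on departure being unrelated to relapse; the documents give neither a loss rate nor an expected six-month rate. The objective is secondary and descriptive, with no threshold attached. The Simon stopping rule and the primary conclusion are unaffected. This is a modest improvement, worth making because it is cheap and because one patient moves the result by roughly 8 to 17 points with 12 down to 6 responders.

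**What to change.** In section 15.2, make the six-month result the Kaplan-Meier estimate of the probability that a response lasts six months, with its 95% CI (for example log-log), taken from the curve already planned. State that responders who leave follow-up in remission are censored at their last response assessment. Show the crude fraction as a supplement, giving its denominator rule and the number censored before month 6.

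The cost is a sentence or two in section 15.2 and no new data. The downside is small: Kaplan-Meier assumes non-informative censoring, and its interval is approximate with about 6 to 12 responders. Reporting the number censored lets a reader judge how much depends on that assumption.
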